5.2. Participant Dispositions

Screened participants and reason for screen failures will be summarized overall.

The number of participants in the following disposition categories will be summarized throughout the study by Nicotine-user, non-Nicotine user groups and overall:

• Participants enrolled (e.g., Participants who fulfilled eligibility criteria at Screening Visit S1 and with CFR ≥2 and ≤3.5 both at Screening Visit S2, and at Week 0.).

^{**} Relative to the day of last administration of the study treatment (guselkumab) within the treatment phase.

^a Baseline

^b If CFR measurement is unsuccessful, 2 attempts to measure a CFR can be made on different days. In such cases, at Weeks 16 and 32 the visit window for the CFR parameter can be extended by 7 additional days (CFR visit window = -7 / +14 days).

^c For participants, who do have a Week 28 assessment, 4 weeks after the last dose of the guselkumab within the treatment phase. For participants who permanently discontinue guselkumab before Week 28, the date of discontinuation. Following the premature termination of the study 4 to 8 weeks after the last dose of guselkumab within the treatment phase.

^d Only for participants, who do have a Week 28 assessment.

^e For participants who receive guselkumab after the treatment phase, the date of the first dose of guselkumab outside of the treatment phase.

- Participants who received study intervention (guselkumab).
- Participants who completed the study.
- Participants who discontinued study intervention (guselkumab).
 - o Reasons for discontinuation of study intervention (guselkumab).
- Participants who terminated study prematurely along with primary reasons.

Listings of participants will be provided for the following categories:

- Participants who discontinued study intervention (guselkumab).
- Participants who terminated study prematurely
- Participants who were enrolled yet did not receive study intervention (guselkumab).

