5.1.1. Visit Windows

Baseline will be defined as the last non-missing measurement prior to or on the day of the first dose of study treatment (guselkumab).

Study day will be calculated as follows:

- Days prior to first dose: Study Day = date treatment first dose date.
- Days on or after first dose: Study Day = date treatment first dose date + 1.

First dose refers to guselkumab.

As participants do not always adhere to the protocol visit schedule, the following rules are applied to assign actual visits to analysis visits. Listed below are the visit windows and the target days for each visit. The reference day is Study Day 1. If a participant has 2 or more actual visits in 1 visit window, the visit closest to the target day will be used as the protocol visit for that visit window. The other additional visit(s) will not be used in the summaries or analyses but they can be used for determination of clinically important endpoints. If 2 actual visits are equidistant from the target day within a visit window, the later visit is used.

The Time Interval (label on output), Time Interval (Day) and the Target Time Point (Day) are indicated in Table 2. If an assessment is not scheduled for every visit, windows will be combined so that the interval between targeted study days is split evenly and consistently between visits.

Table 2: Visit Windows

Scheduled Visit	Time Interval (label on	Planned	Target Time Point	Time Interval	Target Time
Number	output)	Time Point	(Interval for tests)	(Day) *	Point (Day) *
			-42 – -28		
			(Only for		
			pregnancy test)	-42 – -28	-
			-42 – -14		
			(Only for clinical		
			laboratory tests and		
			vital signs [blood		
			pressure,	-42 – -14 (Prior to	
			pulse/heart rate and	Screening	
			temperature])	Visit S2)	-
			- 56 – - 1		
		Screening	(Only for		
		Visit S1	QuantiFERON-TB		
		(Dermatology)	Gold test)		
		(Maximum of	(Within 2 months		
		2 weeks prior	before		
	Screening	to Screening	Week 0)	- 56 – - 1	-
S1	Visit S1	Visit S2)	-841	-841	-

CONFIDENTIAL – FOIA Exemptions Apply in U.S.

	Time				
Scheduled	Interval				
Visit	(label on	Planned	Target Time Point	Time Interval	Target Time
Number	output)	Time Point	(Interval for tests)	(Day) *	Point (Day) *
			(Only for Chest		
			radiograph)		
			(Within 3 months		
			before		
			Week 0)		
			-42 – -14	-4214	-
		Screening			
		Visit S2	07 14		
		(Cardiology)	-27 – -14		
		(Minimum of 2 weeks and	(Only for		
		maximum of 4	pregnancy test, urine nicotine test,		
	Caranina				

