5.3.1. Definition of Endpoint

5.3.1.1. Coronary flow reserve (CFR)

Coronary flow reserve will be measured non-invasively using transthoracic doppler echocardiography, using a high-resolution ultrasound system with a suitable transducer and the respective software. The acoustic window will be around the midclavicular line in the fourth and fifth intercostal spaces in the left lateral decubitus position. Long-axis views of the left ventricle will be obtained, and the ultrasound beam will then be angled laterally and superiorly to image the anterior interventricular groove. The coronary blood flow in the distal portion of the left anterior descending artery (LAD) will be examined with the help of color Doppler flow mapping. A sample volume will be positioned on the color signal in the LAD, and Doppler spectral tracings of flow velocity will be recorded. First, the baseline spectral Doppler signals in the distal portion of the LAD will be recorded. Then 140 µg/kg/min adenosine, a coronary vasodilator, will be administered for 5 minutes. Doppler signals will be recorded continuously at baseline and during the period of adenosine infusion. Measurements of hyperemic coronary flow velocity will be done continuously during the adenosine infusion, and the CFR measurement will be recorded based on the guidelines provided by the cardiology core lab.

Cardiac parameters, along with strain and coronary parameters will be assessed by the cardiology core lab as defined in the process document of the core lab.

The primary endpoint for the study is the change from baseline in CFR at Final Efficacy Visit (Week 32) based on FAS.

Data Handling of Primary Efficacy Endpoint

For most of the secondary efficacy analyses (eg, over time summaries), after the treatment failures are applied, no imputation will be performed for missing data (eg, lost to follow-up, missed study visit) and the values will remain as missing and as observed data will be used for the analysis.

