5.3.2. Estimand

Primary Trial Objective: To evaluate the effect of guselkumab on CFR measured by transthoracic doppler-echocardiography, in participants with moderate-to-severe psoriasis and intermediate cardiovascular risk. Intermediate cardiovascular risk is defined by CFR ≥ 2 and ≤ 3.5 at Screening Visit S2.

Estimand Scientific Question of Interest: What level of change from baseline of CFR considered to have benefited from guselkumab for the pre-specified duration (32 weeks).

Study intervention:

• Guselkumab (100 mg SC [Subcutaneous] injections at Week 0, 4, 12, 20 and 28)

Population: Participants with moderate to severe plaque psoriasis (with or without PsA) for at least 6 months prior to study entry. The target population consists of men or women aged 18 years and above with moderate to severe plaque psoriasis of at least 6 months' duration, defined as psoriasis area and severity index (PASI) \geq 12, and involved body surface area (BSA) \geq 10% at Screening Visit S1 and CFR with \geq 2 to \leq 3.5 at Screening Visit S2. Participants should not be with CFR of \leq 2 or \geq 3.5 at both Screening Visit S2 and Week 0.

Variable: Change from baseline in the CFR measurement at Final Efficacy Visit (Week 32). The CFR measurement at Week 0, Baseline will be considered as baseline value. Participants who had adequate primary endpoint measurements will be assessed at Final Efficacy Visit (Week 32) considering as observed for the analysis.

Summary measure (Population-level summary): Least squares means (LSmeans), together with the 95% CI and p-values based on the MMRM.

Intercurrent events and their corresponding strategies:

Intercurrent Events	Strategy for Addressing Intercurrent Events and Its Description
	Composite Strategy: A participant with this intercurrent event will be excluded from the analysis.

^{*} List of concomitant medications from ADaM datasets will be shared with the clinical team after the receipt of SDTM data by the programming team for each data cut. The clinical team will review the list and flag the appropriate disallowed medications. This list will be used for the intercurrent events.

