5.3.3. Analysis Methods

5.3.3.1. Main Estimator (Analysis) for the Primary Estimand

A MMRM will be used to determine the change from baseline in Cardiovascular measurement at Week 32 or Week 16 in the open label phase to compare the participant groups of nicotine users vs non-nicotine users, will be analyzed using a MMRM based on observed case data. The models will include baseline CFR measurement at Week 0, Baseline before first administration of guselkumab as a covariate, and Nicotine use, BMI, presence or absence of PsA, age, gender, and visit.

The estimates for the primary estimand of the treatment effect of guselkumab will be provided by the difference of change from baseline at Week 32 in the LSmeans. The 95% CI for the differences in LSmeans and p-values will be calculated based on the MMRM. The within-subject covariance between visits will be estimated via an unstructured variance-covariance matrix. In case of convergence problems, alternative variance-covariance structures will be tried in the following order, with the first structure that converges being used in the analysis: heterogeneous Toeplitz, standard Toeplitz, and autoregressive order 1 (AR[1]) with separate subject random effect.

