6.2. Appendix 2 Changes to Protocol-Planned Analyses

The Safety Analysis Set is different in the Protocol.

Safety analysis set defined in the protocol as "All enrolled participants who receive at least 1 dose of guselkumab." Whereas in SAP we have modified the definition as "The safety analysis set includes all participants who received at least 1 dose of adenosine and guselkumab".

The Safety Analysis Set will likely contain more participants than the FAS. It would not be appropriate to define the safety analysis set as participants receiving at least one dose of guselkumab. It is necessary to also capture possible safety related information starting with the first assessment of the Coronary Flow Reserve at visit S2, because it involves use of intravenous Adenosine.

All enrolled participants who receive at least 1 dose of guselkumab, while it is "The full analysis set (FAS) includes all participants who received at least 1 dose of guselkumab." in the current SAP.

In Protocol the primary and secondary efficacy endpoints are performed at Week 32 for CFR, GLS and cfPWV, while in SAP it is appropriately defined to be completed at Final Efficacy Visit (Week 32) as per Table 2. The primary and secondary efficacy endpoints will be analyzed at Final Efficacy Visit (Week 32) with the definition applied as per Table 2 for the last dose after premature termination of the study.

In the protocol The Final Efficacy Visit (Week 32) should occur 4 weeks after the last dose of the guselkumab within the study. Whereas in SAP, following the premature termination of the study 4 to 8 weeks after the last dose of guselkumab within the treatment phase will be used.

In the protocol for participants who prematurely discontinues guselkumab before Week 28, the Final Efficacy Visit (Week 32) should take place at the time of discontinuation, or as soon as possible, and all assessments scheduled for the Final Efficacy Visit (Week 32) should be performed, whereas in the SAP for participants who permanently discontinue guselkumab before Week 28, the date of discontinuation will be used.

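### The SAP drops treated participants under a strategy it misnames composite, and its Week 32 slot can hold much earlier scans with no rule on which visit a scan fills

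*SAP*

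**What the plan says.** **Intercurrent events.** SAP 5.3 bases the primary efficacy analysis on the FAS, which Section 4 defines as everyone with at least one guselkumab dose. The intercurrent-event tables in 5.3.2 and 5.4.1.2 name the strategy composite and describe it as leaving the affected participant out of the analysis. The event itself is not visible in the available text. The footnote to 5.3.2 has the clinical team flag disallowed medications for this purpose at each data cut.

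**Final scans.** Table 2 prints Day 211-256 for CFR, and 211-252 otherwise, for the Final Efficacy Visit (Week 32). Footnote c to that cell ties the visit to the date of discontinuation or, after termination, to the last dose: "Following the premature termination of the study 4 to 8 weeks after the last dose of guselkumab within the treatment phase". Appendix 2 (Section 6.2) makes this operative. The primary and secondary endpoints are analysed "with the definition applied as per Table 2 for the last dose after premature termination of the study"; the interval of "4 to 8 weeks after the last dose of guselkumab within the treatment phase will be used"; and "for participants who permanently discontinue guselkumab before Week 28, the date of discontinuation will be used". Section 5.1.1 adds that for assessments not done at every visit "windows will be combined so that the interval between targeted study days is split evenly and consistently between visits".

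The endpoint follows the footnote's label: "The primary endpoint for the study is the change from baseline in CFR at Final Efficacy Visit (Week 32) based on FAS". The estimand question, however, is set "for the pre-specified duration (32 weeks", and the estimator in 5.3.3.1, repeated in 5.4.1.3, is "the difference of change from baseline at Week 32 in the LSmeans", from an MMRM with visit as a term.

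**The concern.** A composite strategy builds the event into the outcome. Removing the person does not. It also makes the analysed set smaller than the FAS, selects on something that happens after baseline, and throws away measurements made before the event. Appendix 2 itself says that few participants remain.

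For the scans, the slot matters because the model estimates change by visit, and the terms listed in 5.3.3.1 include neither actual study day nor number of doses. If early final scans sit in the Week 32 slot, the least squares mean averages over different treatment durations while the estimand speaks of 32 weeks. If a scan meets two visit definitions and nothing says which wins, two programmers can build different datasets from the same SAP. SAP 1.2 adds weight: after 31 May 2023 only final visits were scheduled, and the sponsor sometimes advised against a per-protocol visit so as to avoid two cardiovascular assessments close together. A final scan may therefore be a participant's only post-baseline one.

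**Working it through.** **Table 2's own figures.** First dose is Day 1, so nominal day = 7 × week + 1. Week 16 = 113, Week 28 = 197, Week 32 = 225, Week 40 = 281. The protocol windows around Day 225 are 218-232 (±7) and 218-239 (-7/+14). Midpoints (197 + 225)/2 = 211 and (225 + 281)/2 = 253 give 211-252. All match Table 2. The CFR upper limit of 256 is not a midpoint and is taken as printed.

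**Footnote c after termination.** Scan day = last-dose day + 28 to + 56; weeks on study = (day - 1)/7.

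| Last dose | Dose day | Final scan, days | Weeks on study | Within CFR 211-256? |
|---|---|---|---|---|
| Week 0 | 1 | 29-57 | 4-8 | No |
| Week 4 | 29 | 57-85 | 8-12 | No |
| Week 12 | 85 | 113-141 | 16-20 | No |
| Week 20 | 141 | 169-197 | 24-28 | No |
| Week 28 | 197 | 225-253 | 32-36 | Yes |

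Allowing the ±7-day dose window, the latest scan after a Week 20 dose is Day 141 + 7 + 56 = 204, still before 211. Day 253 is one day past the 252 limit for GLS and cfPWV. The discontinuation clause sets no minimum day.

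**Double qualification.** The printed Week 16 window is Day 100-129 for CFR and 100-125 for GLS and cfPWV. After a Week 12 last dose the final scan can fall on 141 - 113 + 1 = 29 nominal days. CFR overlap: 129 - 113 + 1 = 17 days. GLS/cfPWV overlap: 125 - 113 + 1 = 13 days. The tie-break in 5.1.1 deals with two visits in one window, not one visit that meets two definitions.

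**Three rules, three answers.** Combined cut points for the cardiology schedule are (1 + 113)/2 = 57 and (113 + 225)/2 = 169, so Week 16 = Day 58-169 and Week 32 starts at Day 170. Take a CFR scan on Day 135 after a Week 12 last dose. The printed rows put it in Week 20, where no cardiology is planned; the combined rule puts it in Week 16; footnote c puts it in Week 32. Footnote c's own clauses can also collide: Protocol 7.1 lists sponsor termination among the reasons for discontinuing guselkumab, so one participant can meet both the date-of-discontinuation clause and the 4-to-8-week clause.

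**Intercurrent events.** No arithmetic applies. Section 4 and 5.3 keep everyone with one dose; 5.3.2 and 5.4.1.2 remove some of them. Both cannot hold, and the strategy's name fits neither.

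**The case against.** The strongest reply is that footnote c is a disclosed salvage rule, not an oversight. Appendix 2 declares it, the visit at discontinuation comes from the protocol, and both the endpoint and the estimand's variable carry the Final Efficacy Visit label. P-values are nominal, Section 3 calls the sample size calculation no longer relevant, and 5.6.1 already summarises treatment duration and number of injections. The specific footnote can also be read as overriding the general windows. Most of this stands: a reader might infer a hidden change or a false confirmatory claim, and the documents support neither. What it leaves open is the estimand question and the estimator, which still say 32 weeks, and a precedence that must be guessed.

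A reader might also conclude that study-day windows should replace footnote c as the main analysis. The documents do not make that a clear gain. Under the printed windows, CFR scans on Days 29-99 and 130-210 enter neither modelled visit, so participants could leave the MMRM altogether. The combined Week 16 window runs from (58 - 1)/7 = 8.1 to (169 - 1)/7 = 24.0 weeks, which moves the mixing to another slot.

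On intercurrent events, the reply is that this is mainly a naming error, possibly affecting nobody. The number may indeed be zero. But the stated action is exclusion, so a new name alone would not restore the FAS.

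**Conclusion.** Wrong as written, and worth fixing. The exclusion rule misnames its strategy and contradicts the FAS. That holds whatever the event is; that it is disallowed medication is an inference from the footnote to 5.3.2.

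For final scans, four of the five possible last doses give nominal scan ranges wholly outside the printed Week 32 CFR interval, so the stated question and estimator do not describe what would be estimated. For 17 of 29 possible days after a Week 12 last dose (13 of 29 for GLS and cfPWV), a scan fits two visits.

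The day ranges rest on nominal dosing days and are possibilities, not observations. They are not a continuous run: Days 86-112 and 142-168 are not reached nominally under the 4-to-8-week clause. No passage shows a participant whose last dose at termination was Week 0, or gives counts by last dose. It would be tempting to infer that the Week 32 estimate is diluted by a known amount, or that a scan will be entered twice. Neither is supported: the size and direction of any bias cannot be estimated, and the SAP is silent on double entry rather than prescribing it.

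**What to change.** **Intercurrent events.** Keep the participant in the FAS. Either use all observed values (treatment policy) or set only post-event values to missing (hypothetical); name the choice correctly and run the other as a sensitivity analysis. Finalise the event flags before database lock without access to CFR results; Section 6.4 already sets that timing for major deviations, including prohibited medication. Under the hypothetical option, data are added only for participants with a post-baseline scan before the event.

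**Final scans.** State in 5.1.1 that each scan fills one slot, and which rule takes precedence among footnote c's clauses, the printed intervals and the combined windows. If footnote c stays the main rule, call the result change at the Final Efficacy Visit, not Week 32, in 5.3.2, 5.3.3.1, 5.4.1 and 5.4.1.3, and report weeks on study at the scan. Add a sensitivity MMRM that assigns scans by actual study day (Week 32 = Day 211-256 for CFR, 211-252 for GLS and cfPWV), and state how many scans and participants drop out.

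**Cost.** SAP wording, derivation code and a little more analysis. The wider interval from using fewer scans is confined to the sensitivity run.

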5.3. Primary Endpoint Analysis

The efficacy analysis of the primary endpoint will be based on the FAS.

5.3.1. Definition of Endpoint

5.3.1.1. Coronary flow reserve (CFR)

Coronary flow reserve will be measured non-invasively using transthoracic doppler echocardiography, using a high-resolution ultrasound system with a suitable transducer and the respective software. The acoustic window will be around the midclavicular line in the fourth and fifth intercostal spaces in the left lateral decubitus position. Long-axis views of the left ventricle will be obtained, and the ultrasound beam will then be angled laterally and superiorly to image the anterior interventricular groove. The coronary blood flow in the distal portion of the left anterior descending artery (LAD) will be examined with the help of color Doppler flow mapping. A sample volume will be positioned on the color signal in the LAD, and Doppler spectral tracings of flow velocity will be recorded. First, the baseline spectral Doppler signals in the distal portion of the LAD will be recorded. Then 140 µg/kg/min adenosine, a coronary vasodilator, will be administered for 5 minutes. Doppler signals will be recorded continuously at baseline and during the period of adenosine infusion. Measurements of hyperemic coronary flow velocity will be done continuously during the adenosine infusion, and the CFR measurement will be recorded based on the guidelines provided by the cardiology core lab.

Cardiac parameters, along with strain and coronary parameters will be assessed by the cardiology core lab as defined in the process document of the core lab.

The primary endpoint for the study is the change from baseline in CFR at Final Efficacy Visit (Week 32) based on FAS.

Data Handling of Primary Efficacy Endpoint

For most of the secondary efficacy analyses (eg, over time summaries), after the treatment failures are applied, no imputation will be performed for missing data (eg, lost to follow-up, missed study visit) and the values will remain as missing and as observed data will be used for the analysis.

5.3.2. Estimand

Primary Trial Objective: To evaluate the effect of guselkumab on CFR measured by transthoracic doppler-echocardiography, in participants with moderate-to-severe psoriasis and intermediate cardiovascular risk. Intermediate cardiovascular risk is defined by CFR ≥ 2 and ≤ 3.5 at Screening Visit S2.

Estimand Scientific Question of Interest: What level of change from baseline of CFR considered to have benefited from guselkumab for the pre-specified duration (32 weeks).

Study intervention:

• Guselkumab (100 mg SC [Subcutaneous] injections at Week 0, 4, 12, 20 and 28)

Population: Participants with moderate to severe plaque psoriasis (with or without PsA) for at least 6 months prior to study entry. The target population consists of men or women aged 18 years and above with moderate to severe plaque psoriasis of at least 6 months' duration, defined as psoriasis area and severity index (PASI) \geq 12, and involved body surface area (BSA) \geq 10% at Screening Visit S1 and CFR with \geq 2 to \leq 3.5 at Screening Visit S2. Participants should not be with CFR of \leq 2 or \geq 3.5 at both Screening Visit S2 and Week 0.

Variable: Change from baseline in the CFR measurement at Final Efficacy Visit (Week 32). The CFR measurement at Week 0, Baseline will be considered as baseline value. Participants who had adequate primary endpoint measurements will be assessed at Final Efficacy Visit (Week 32) considering as observed for the analysis.

Summary measure (Population-level summary): Least squares means (LSmeans), together with the 95% CI and p-values based on the MMRM.

Intercurrent events and their corresponding strategies:

Intercurrent Events	Strategy for Addressing Intercurrent Events and Its Description
	Composite Strategy: A participant with this intercurrent event will be excluded from the analysis.

^{*} List of concomitant medications from ADaM datasets will be shared with the clinical team after the receipt of SDTM data by the programming team for each data cut. The clinical team will review the list and flag the appropriate disallowed medications. This list will be used for the intercurrent events.

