Open-label Treatment Phase END OF STUDY 20 16 28 32 40 S1 Derm **S2** Cardio PE Treatment Cohort: Nicotine Users (n=20) Nicotine Non-users (n=30) = Cardiology Assessments (cfPWV, GLS and CFR) = Biomarker Assessments Visit Window between Screening Visit 1 and Screening Visit 2 = maximum of 2 weeks $Visit\ Window\ between\ Screening\ Visit\ 2\ and\ Week\ 0=minimum\ of\ 2\ weeks\ and\ maximum\ of\ 4\ weeks\ CFR,\ GLS\ and\ cfPWV\ measurements\ at\ Week\ 0\ will\ be\ considered\ as\ the\ baseline\ measurements\ at\ Week\ 0\ will\ be\ considered\ as\ the\ baseline\ measurements\ at\ Week\ 0\ will\ be\ considered\ as\ the\ baseline\ measurements\ at\ Week\ 0\ will\ be\ considered\ as\ the\ baseline\ measurements\ at\ Week\ 0\ will\ be\ considered\ as\ the\ baseline\ measurements\ at\ Week\ 0\ will\ be\ considered\ as\ the\ baseline\ measurements\ at\ Week\ 0\ will\ be\ considered\ as\ the\ baseline\ measurements\ at\ Week\ 0\ will\ be\ considered\ as\ the\ baseline\ measurements\ at\ week\ 0\ will\ be\ considered\ at\ the\ baseline\ measurements\ at\ week\ 0\ will\ be\ considered\ at\ the\ baseline\ th$ cfPWV = carotid-femoral pulse wave velocity: CFR = coronary flow reserve; GLS = global longitudinal strain; PE = Primary Endpoint; S1 = Screening Visit 1 (Dermatology Assessments); S2 = Screening Visit 2 (Cardiology Assessments); SE = Secondary Endpoint

Figure 1: Schematic Overview of Study Design

The study is prematurely discontinued on 31st of May 2023,

- All data collected will be analyzed and therefore, all data will need to go through data cleaning process.
- Before the 31st of May 2023, per protocol visits can be scheduled, this allows sites to decide for continued patient treatment, either on commercial guselkumab or any other treatment
- o After the 31st of May 2023 only the Final Efficacy visits, and Final Safety visits are to be scheduled.
- There are instances where the sponsor recommends not to do the per-protocol visits prior to 31st of May in case this results in too much patient burden in terms of assessments e.g., 2 cardiovascular assessments in a short timeframe.

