5.4.1.1. Definition of Endpoint(s)

Refer to Section 5.3.1 for Definition of CFR Endpoint

The secondary endpoint for the study is the change from baseline in CFR at Week 16 or GLS/cf-PWV at Week 16 and Week 32 are based on FAS.

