6.9. Appendix 9 Medications of Special Interest

A listing of concomitant medications (excel file) will be provided by the ClinChoice programming team with treatment start date, study day, and duration to the sponsor clinical team to identify the disallowed medication and medication of special interest in the study. During the study the spreadsheet will be updated for every data cut and the list with flagging will be updated accordingly.

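### The SAP labels its intercurrent-event rule composite, but the rule removes the participant, so results announced on the FAS would come from an undeclared subset

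*SAP*

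**What the plan says.** SAP 5.3.2 (primary estimand) and SAP 5.4.1.2 (secondary estimand) give the same rule: "Composite Strategy: A participant with this intercurrent event will be excluded from the analysis".

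The column naming the event cannot be read in the supplied text. In 5.3.2 a footnote explains how events are found: concomitant medications are listed at each data cut, and "The clinical team will review the list and flag the appropriate disallowed medications". SAP Appendix 9 describes the file, which goes to the sponsor "with treatment start date, study day, and duration to the sponsor clinical team to identify the disallowed medication". I therefore take the event in 5.3.2 to be use of a disallowed medication, and I assume the same event in 5.4.1.2, where no footnote is visible.

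On the analysis set, SAP 5.3 states: "The efficacy analysis of the primary endpoint will be based on the FAS". SAP 5.3.1.1 repeats it: "The primary endpoint for the study is the change from baseline in CFR at Final Efficacy Visit (Week 32) based on FAS". SAP 5.4.1.1 says that the secondary cardiology endpoints "at Week 16 and Week 32 are based on FAS". SAP Appendix 2 gives the definition, in line with SAP section 4: "The full analysis set (FAS) includes all participants who received at least 1 dose of guselkumab". SAP section 4 defines only three sets: screened, FAS and safety.

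**The concern.** The label and the action describe different analyses. Under a composite strategy, a participant with the event stays in and the event determines or changes the outcome value, so a value must be specified. Neither section specifies one. Removing the participant is a different operation and answers a question about people who never had the event.

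The action also conflicts with the announced analysis set. Membership of the FAS is settled by the first dose. The exclusion depends on something that happens after it, so the analysed group is selected on a post-baseline event while the table title says FAS. A reader of the report could not tell.

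Two things are at stake: what the primary estimate describes, and the loss of readings from a sample that SAP Appendix 2 already calls low after early termination. Under protocol 7.1, a participant given a prohibited medication must stop guselkumab and have a Final Efficacy Visit at that time or as soon as possible. Those readings would be collected and then discarded.

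**Working it through.** **The passages side by side**

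1. SAP 5.3, 5.3.1.1 and 5.4.1.1: analysis on the FAS.
2. SAP section 4 and Appendix 2: FAS means at least one dose of guselkumab, with no exception for later events.
3. SAP 5.3.2 and 5.4.1.2: participants with the event leave the analysis.
4. SAP section 4: no per-protocol or similar set exists in which (3) could be carried out.
5. SAP Appendix 2 (changes to protocol-planned analyses): the exclusion is not listed.
6. SAP Appendix 4: intake of prohibited medication is a major deviation, to be summarised and listed. Exclusion is not mentioned.

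If even one dosed participant has the event, (1) and (3) cannot both be carried out. This holds whatever the unreadable cell says.

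**Readings before the event.** The rule is worded per participant, not per visit. The model in SAP 5.3.3.1 is an MMRM on observed cases, so it could use a Week 16 value from someone whose event came later. Unless the unseen cell limits timing, that value is lost too.

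**Scale.** The plan gives no expected number or timing of events, so there is no figure of its own to reproduce. All inputs below are assumptions: event share p of 5%, 10% or 20%; share f of events falling after Week 16; correlation r between the Week 16 and Week 32 changes of 0.3 to 0.7. The reference is an analysis with both readings for everyone.

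- Exclusion, either visit: SE ratio = 1/√(1 − p).
- Date-based rule (only readings after first flagged use set to missing), Week 16: 1/√(1 − p(1 − f)).
- Date-based rule, Week 32, all events after Week 16, maximum likelihood using every Week 16 value: √((1 − r²)/(1 − p) + r²).

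| p | Exclusion | Date-based, Week 16, f = 0.5 | Date-based, Week 32, r = 0.3 / 0.5 / 0.7 |
|---|---|---|---|
| 5% | 1.026 | 1.013 | 1.024 / 1.020 / 1.013 |
| 10% | 1.054 | 1.026 | 1.049 / 1.041 / 1.028 |
| 20% | 1.118 | 1.054 | 1.108 / 1.090 / 1.062 |

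Example: p = 0.20, r = 0.5 gives √(0.75/0.80 + 0.25) = √1.1875 = 1.090. At Week 16 the date-based rule loses nothing if all events come later (f = 1) and gains nothing over exclusion if all come earlier (f = 0). In a simulation without covariates, with an assumed 20 participants, r = 0.3 and 20% events, the Week 32 ratios were 1.112 (date-based) and 1.114 (exclusion), so in a small sample that gain nearly vanishes.

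In CFR units, take the planning SD of 0.8 (SAP section 3), an assumed 20 participants and a simple one-sample t interval. The 95% half-width rises from 0.374 to 0.398 with 18 left, or 0.426 with 16 left.

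**Direction.** If participants without the event change by 0.30 on average and 20% have the event, the full-FAS mean is 0.8 × 0.30 + 0.2 × m. With m = 0 this is 0.24; with m = 0.5 it is 0.34. Exclusion reports 0.30 in both cases. Protocol Table 1 prohibits drugs that raise CFR as well as drugs that lower it, so the sign cannot be settled from the documents.

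**The case against.** The best defence is that the FAS is only the starting set. The SAP says openly that it analyses observed readings from participants with adequate measurements, so a dosed participant without a usable post-baseline value is outside the model anyway. The exclusion is disclosed in the estimand section, so perhaps only a linking sentence is missing. Part of this stands: the rule is not hidden, and an observed-case MMRM never uses literally everyone. But a reading that was never taken differs from one that was taken and then removed because of a post-baseline event, and the composite label remains wrong either way.

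The documents do not support several stronger readings that a reader might reach:

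- *The rule breaks a promise to analyse everything.* SAP 1.2 does say "All data collected will be analyzed and therefore, all data will need to go through data cleaning process". That bullet concerns data cleaning after termination, and the SAP narrows it elsewhere: exploratory endpoints are listed only (5.5) and biomarkers are not analysed (Appendix 2). The FAS conflict carries the point without it.
- *Valid Week 16 readings will certainly be lost.* This depends on the unseen cell, which may limit timing. The gap in the supplied text is not an error in the plan.
- *The estimate is biased in guselkumab's favour.* Neither size nor sign can be derived.
- *The flagging is steered by results.* Nothing says so. The SAP simply does not require the review to be done without sight of outcomes, and Appendix 4 already identifies major deviations before database lock.
- *Only a date-based rule is acceptable.* It is one of several sound choices, and its gain at Week 32 is small.

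**Conclusion.** The point holds as a contradiction within the SAP. In 5.3.2 and 5.4.1.2 the strategy named is not the strategy applied, and the strategy applied does not fit the analysis set announced in 5.3, 5.3.1.1 and 5.4.1.1. This does not depend on which event the table names. That the event is disallowed medication is inferred from the footnote and Appendix 9 for the primary estimand, and assumed for the secondary one.

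The cost in precision is modest: about 2.6% to 11.8% on the standard error for assumed event shares of 5% to 20%. No bias figure is claimed. P-values are nominal (SAP 5.1), so the main harm is to what the primary estimate means. It should be corrected before results are reported.

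**What to change.** In SAP 5.3.2 and 5.4.1.2, make label, action and analysis set agree.

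1. Remove the participant-level exclusion. Run the MMRM on all FAS participants with all observed readings, and label it treatment policy.
2. As an alternative main analysis, or in support, use a date-based rule labelled hypothetical strategy: only readings after the first flagged use are set to missing. Participants whose first flagged use precedes Week 16 then contribute no post-baseline reading; report their number.
3. If the exclusion analysis is kept, present it as supplementary on a named subset, not as the FAS result.
4. Complete the flagging before database lock, without reference to CFR, GLS or cfPWV results.

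The cost is SAP wording and one extra MMRM table. No new data are needed, because the Appendix 9 file already holds start date, study day and duration. There are two drawbacks. The treatment-policy analysis includes readings taken on drugs that, according to protocol 6.5.3, may affect CFR. The date-based analysis assumes readings are missing at random after the event. Showing both lets the reader judge how much either matters.
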